**Research Application:**

**A. Type of Study: Human**

**B. Brief Summary of Proposal:**

**(1) Project Background:** Mesothelioma is a rare, aggressive and treatment-resistant disease and, in the United States, is caused almost exclusively by exposure to asbestos fibers. Although predominantly associated with the pleura of the lung and peritoneum, mesothelioma may also develop in a variety of other locations in which mesothelial tissue exists including pericardium and tunica vaginalis testis. There is often a lengthy latency period of 40-50 years between exposure and disease onset. The median age of diagnosis is 65 years while the median survival time after diagnosis without treatment is 9 months. Symptoms, where present, may be non-specific, which further contributes to delayed diagnosis. Because patients with mesothelioma may be asymptomatic until very late in the course of their disease, they may have very limited therapeutic options available because advanced disease is less amenable to treatment. With interventions, survival is extended only to 12 months. As a result, patient prognosis is poor, and mesothelioma carries with it a high mortality rate. Further compounding this issue is the fact that the incidence of mesothelioma is low (approximately 2 per 100,000 capita) in comparison with other types of cancer and as a result, little research has been conducted on either the early identification or early treatment of disease. The ability to identify the presence of disease at an early stage or increase clinical suspicion for the presence of disease among asbestos exposed individuals, would enable earlier detection and earlier treatment, thus reducing morbidity and mortality. In this study, the volatile organic compound (VOC) profile from subjects with histologically confirmed mesothelioma will be compared against case-matched control subjects with bilateral pleural plaques or bilateral pleural thickening. Putative markers will then be tested against a blinded cohort to test predictive value of the markers.

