**(2) Project Rationale:** This study seeks to identify markers for mesothelioma using a non-invasive technique which samples volatile organic compounds (VOC) in the breath of test subjects (Owlstone Medical Ltd, Cambridge, England). A comparison will be made with an FDA-approved, serum-based assay (Lumipulse Mesomark, Fujirebio Diagnostics Inc., Malvern, PA). Identifying patients who are either predisposed to developing mesothelioma by pleural findings as an indication of asbestos exposure or who may be at an early disease stage, is expected to improve prognosis by limiting disease progression through more effective medical and surgical therapeutics.

**(3) Purpose of Study and/or Hypothesis:** Individuals with pleural mesothelioma are anticipated to have a different volatile organic compound (VOC) profile in comparison with appropriately matched controls. These specific compounds may have a diagnostic potential which enables the early detection of patients with disease before overt clinical symptoms become manifest. Following the identification of putative

biomarkers, the predictive capability of these markers alone and in concert with a serum-based assay, will be tested.

**(4) Anticipated Outcome:** We anticipate that one or more VOC markers in breath samples from affected subjects will be identified using the Owlstone Breath Biopsy sampling methodology which will show an association with the presence of pleural mesothelioma in patients. Furthermore, we will evaluate participant's Lumipulse Mesomark serum assay, comparing those results with the VOC profile to discern parameters of efficacy.

**(5) Importance/Relevance:** Identifying patients who are either likely to develop mesothelioma or who are at an early disease stage, is expected to improve prognosis by limiting disease progression through more effective medical and surgical therapeutics.

**C. References and Supporting Data:** See accompanying Owlstone's Breath Biopsy® The Complete Guide Second Edition as part of this IRB submission and the two 2004 American Radiology Letters to the Editor consisting of a response to a peer-reviewed article on chest radiograph B-readers and the author's reply.

**D. Detailed Plan of Proposed Research:** As submitted in the IRB A-1 Research Application document.

**E. Specific Objectives or Aims:** Specific Aim 1: Identify putative VOC biomarkers in the breath samples of subjects with mesothelioma in comparison with case-matched controls.

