Specific Aim 2: Test the predictive capability of VOC biomarkers and serum-based mesothelioma biomarkers both individually and collectively.

**F. Experimental Design:** This will be a prospective, non-randomized, case-controlled study. In Specific Aim 1, the disease status of the study population will not be blinded to the investigators in order to select disease-specific biomarkers. In Specific Aim 2, the Investigators and the analytics team will be blinded to the presence of disease to determine the predictive value of the markers. Predictive capability will be defined by determining the sensitivity, specificity and positive and negative predictive capability of the selected VOC biomarkers in identifying subjects with mesothelioma. In addition, study subjects will also be tested with an FDA approved, serum-based ELISA assay (Lumipulse, Mesomark, Fujirebio). The predictive capabilities of both tests will be evaluated both individually and collectively.

Phase 1 - Discovery of VOCs associated with the presence of mesothelioma: A total of 200 volunteers - 100 with objective evidence of exposure to asbestos and no evidence of mesothelioma, and 100 with histologically confirmed evidence of mesothelioma - will be recruited into this phase of the study with an expected study duration of up to 24 months. Objective evidence of asbestos exposure for purposes of this study include, but may not be limited to, a history of exposure to asbestos and bilateral pleural plaques or bilateral pleural thickening. Radiographic evidence of exposure will be rendered by an A reading, B reading, or an interpretation of a radiologist board certified by the American College of Radiology.

Phase 2 - Validation study to assess the predictive capability, sensitivity and specificity of selected VOCs in identifying subjects with mesothelioma: A total of 100 volunteers - 65 with objective evidence of

asbestos exposure and no evidence of mesothelioma, and 35 with objective evidence of mesothelioma - will be recruited into this phase of the study with an expected duration of up to 12 months. The investigators and testing laboratories will be blinded as to the presence of mesothelioma among the participants.

Phase 2 is contingent on the successful identification of VOCs during the Phase 1 discovery study. If no putative biomarkers are identified in Phase 1 of this study or if the predictive capability proves to be too low, the study will be discontinued.

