#### I. Time/Task Summary for study procedures

#### TIME TASK SUMMARY

STUDY DESIGN/APPROVAL

----->

PHASE 1 – Determination of VOC markers

PHASE 2 – Predictive capability of VOC markers

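### The stop rule uses a definition of predictive capability that includes PPV and NPV, which at 50% and 35% recruited cases reflect the recruitment mix and not predictive value in asbestos-exposed people

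*Combined protocol and SAP*

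**What the plan says.** Section F gives two grounds for discontinuing: no putative markers found in Phase 1, "or if the predictive capability proves to be too low, the study will be discontinued". The sentence before it makes Phase 2 conditional on VOCs being identified in Phase 1. The second ground names no threshold, deciding measure or set of subjects.

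The term has a definition earlier in Section F: "Predictive capability will be defined by determining the sensitivity, specificity and positive and negative predictive capability of the selected VOC biomarkers". I read positive and negative predictive capability as PPV and NPV.

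Recruitment is by disease status. Phase 1 takes "100 with objective evidence of exposure to asbestos and no evidence of mesothelioma, and 100 with histologically confirmed evidence of mesothelioma". Phase 2 takes 100 people, 35 with mesothelioma and 65 exposed without it.

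The assessment itself is mostly described as Phase 2 work. Section F calls Phase 2 a "Validation study to assess the predictive capability, sensitivity and specificity of selected VOCs", and the Time/Task Summary sets "PHASE 1 – Determination of VOC markers" against "PHASE 2 – Predictive capability of VOC markers". Section H(3) also mentions predictive capability of the breath test but names no phase. Section D refers the detailed plan to an IRB A-1 application, which is not among the documents supplied.

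**The concern.** In a sample recruited by disease status, sensitivity and specificity can be estimated directly, because each is calculated within cases or within controls. PPV and NPV cannot be read off in the same way: they combine the two groups, and the sponsor chose the group sizes. A PPV from a sample that is half cases says little about a positive result in an asbestos-exposed person, whose chance of disease is not 50% or 35%. The plan makes such values part of the definition on which stopping turns and part of what Aim 2 sets out to measure.

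The second difficulty is where the gate's figure comes from. If it is a Phase 1 figure, the only study data are the 200 subjects from whom the VOCs are chosen, and no part of them is set aside for measuring accuracy.

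Two things are at stake. The first is the go/no-go decision, which commits up to 12 months and the breath kits for 100 subjects (100 × $300 = $30,000, Section H). The second is how the reported PPV and NPV will be read. Blinded Phase 2 sensitivity and specificity are not affected by this point.

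**Working it through.** The documents state no sensitivity, specificity, PPV, NPV or threshold, so there is no figure of the plan's own to reproduce beyond the group totals: 100 + 100 = 200 and 35 + 65 = 100.

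**Inputs from Section F.** Case share p = 100/200 = 0.50 in Phase 1 and 35/100 = 0.35 in Phase 2.

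**Assumption.** The test's accuracy, varied below with sensitivity (Se) equal to specificity (Sp).

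**Formulas.** PPV = Se·p / [Se·p + (1 − Sp)(1 − p)]; NPV = Sp(1 − p) / [Sp(1 − p) + (1 − Se)p].

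**Worked case, Se = Sp = 0.70.**
- Phase 1: PPV = 70/(70 + 30) = 0.70; NPV = 70/(70 + 30) = 0.70.
- Phase 2: PPV = 24.5/(24.5 + 19.5) = 0.557; NPV = 45.5/(45.5 + 10.5) = 0.8125.

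| Se = Sp (assumed) | Phase 1 PPV / NPV | Phase 2 PPV / NPV |
|---|---|---|
| 0.50 (worthless) | 0.50 / 0.50 | 0.35 / 0.65 |
| 0.60 | 0.60 / 0.60 | 0.45 / 0.74 |
| 0.70 | 0.70 / 0.70 | 0.56 / 0.81 |
| 0.80 | 0.80 / 0.80 | 0.68 / 0.88 |
| 0.90 | 0.90 / 0.90 | 0.83 / 0.94 |

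In each row the test is the same and only the recruited mix differs. PPV falls and NPV rises, by less as accuracy improves. The first row shows that an NPV of 0.65 in Phase 2 carries no information about the test.

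The values cannot be re-weighted from the documents. The one frequency given is an incidence of about 2 per 100,000 people (Section B), which is not a prevalence among asbestos-exposed people.

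**If the gate is judged on the Phase 1 subjects.** The documents give neither the number of VOCs nor the panel size, and do not say how markers would be scored. The following simulation therefore rests on assumptions throughout: 100 case-control pairs, normally distributed VOCs with no true difference, ranking by t-test, a linear discriminant score, and the cut-off that maximises the smaller of Se and Sp, with 500 runs per setting. The table gives the share of runs in which pure noise reaches 0.70 on both measures when scored on the selecting subjects.

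| VOCs, number selected | Pair correlation 0 | Pair correlation 0.3 |
|---|---|---|
| 20, 1 | 0% | 0% |
| 20, 5 | 0% | 0% |
| 100, 5 | 2% | 0% |
| 500, 5 | 24% | 3% |
| 500, 10 | 94% | 54% |
| 500, 20 | 100% | 99% |

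A single selected noise VOC never reached 0.70 on both. With selection and cut-off repeated inside each cross-validation fold and pairs kept together, noise reached 0.70 on both in 0 of 500 runs in every setting tried (20 to 1000 VOCs, panels of 1 to 20). Optimism thus ranges from negligible to decisive, and the documents do not show where this study would fall.

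**The case against.** The strongest reply is that the change in PPV between phases shows no wrong decision. The rule would be judged once, at one mix. At a fixed mix, PPV and NPV rise with sensitivity and specificity, so a bar could be set to suit that mix, and the documents contain no PPV or NPV bar to misapply. This stands. A reader might infer from 0.70 falling to 0.56 that the study would wrongly stop or continue; the documents do not support that. What remains is that these values say nothing about predictive value in exposed people, although they sit in a definition that invites that reading.

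A reader might also infer that the rule contradicts the design, because predictive capability is measured only in blinded Phase 2, after which nothing is left to discontinue. That goes too far. The preceding sentence makes Phase 2 contingent on Phase 1, so a Phase 1 gate is the natural reading, and Section H(3) ties the statistic to no phase. The missing subjects and threshold are missing detail rather than a contradiction.

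Nor do the documents say that VOCs will be scored on the subjects who selected them. The high false-pass rates need about 500 VOCs and panels of 10 or more, whereas Section B(4) expects one or more markers. Blinded Phase 2 would in any case expose a false marker.

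Finally, a wrong stop would not remove all serum evidence. Blood is required under eligibility criteria common to both aims, and the serum assay is not selected on Phase 1 data, so it could be evaluated in the 200 Phase 1 subjects. The blinded Phase 2 replication and the validated combination of the two tests would be lost.

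**Conclusion.** The point holds in limited form. The definition of predictive capability, and through it the second ground for stopping, includes two measures that in this design reflect the recruited case share. That follows from the group sizes in Section F and does not depend on which VOCs are chosen or which phase is meant. Its size depends on the assumed accuracy: at 0.70/0.70, PPV/NPV is 0.70/0.70 at the Phase 1 mix and 0.56/0.81 at the Phase 2 mix.

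The Phase 1 optimism is a conditional risk. It arises only if accuracy is scored on the selecting subjects, and its size cannot be fixed from the documents. The change should be made before Phase 1 is analysed. If the A-1 application already sets the gate, that part of the point is met by citing it.

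**What to change.** In Sections F and G:

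- Define predictive capability, for the stop rule and for Aim 2, by sensitivity and specificity. Report PPV and NPV only at a stated prevalence among exposed people, or over a range of prevalences, and not from the 50% or 35% recruitment mix.
- State which subjects the second ground for stopping is judged on. If they are the Phase 1 subjects, estimate sensitivity and specificity by cross-validation, repeating VOC selection and cut-off inside each fold and keeping matched sets together, and compare them with a minimum fixed before the Phase 1 analysis.
- If the A-1 application already contains the rule, cite it here.

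The cost is a few sentences and some computing; recruitment does not change. Phase 1 figures will look lower, and PPV at a realistic prevalence will look less favourable. A strict bar can also stop a weak real marker. As an illustration under assumed conditions (5-fold cross-validation, a bar of 0.60 on both measures, one real VOC with AUC 0.70 among 500), the marker passes in 75% of runs when used alone but in 25% when it sits in a 5-VOC panel, while noise passes in 0% to 1.6%. A team that wants a permissive discovery gate can set a low bar, provided it is set in advance.

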#### **Inclusion Criteria**

- Male or Female subjects over the age of 18
- Reported prior exposure to asbestos
- Radiologically confirmed bilateral pleural plaques or bilateral pleural thickening, or histologically confirmed mesothelioma

#### **Exclusion Criteria**

- Presence of any other malignancies within the past 6 months
- Treatment of any malignancies within the past 6 months
- Unwilling or unable to provide past clinical data
- Unwilling or unable to participate in the breath collection aspect of the study
- Unwilling or unable to provide a blood sample
- Eating, smoking, inhalation of nebulized medication or consuming alcohol within the 2 hours prior to breath and serum collection

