The following inclusion and exclusion criteria will apply to both Specific Aim 1 and 2 of this study.

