**The following demographic and clinical information will be collected for both Phase 1 and Phase 2 of this study:**

#### **Cardinal Demographic and Clinical Features**

- Gender
- Age
- Race/Ethnicity
- Occupations
- Date of first asbestos exposure
- Highest education completed. One year of apprenticeship equals one year of college
- Height
- Weight
- Co-morbidities
- Social Hx (smoking, drinking, recreational drug use)
- Current list of medications, including OTC and “natural” remedies

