### **Case-Matched Controls**

- Age
- Gender
- Ethnicity
- Co-morbidities
- Presence of benign responses to asbestos exposure (Plaques, pleural thickening, etc.)
- Smoking status

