### **Potential Test confounders**

- When did you last smoke
- When did you last drink and what was it
- When did you last eat and what was it
- Time since brushing teeth, or rinsing with anything other than distilled water
- Nebulized inhaled medication less than 2 hours prior to breath collection

**G. Data Analysis:** Phase 1, which is designed to identify putative VOC markers, will be non-randomized and non-blinded. Statistical analysis will be performed by both the Owlstone and Fujirebio laboratories using their trained biostatisticians. Selected biomarkers will then be used in Phase 2. Study subjects in Phase 2 will be anonymized and the Owlstone and Fujirebio laboratory staff will be blinded with regards to disease presence.

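### Among inhaled medicines, the pre-sampling exclusion and the confounder list name only nebulized ones, so recent use of any other inhaler is allowed and its timing is never recorded

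*Combined protocol and SAP*

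**What the plan says.** The last exclusion criterion in section F covers what a subject may not have done shortly before sampling: "Eating, smoking, inhalation of nebulized medication or consuming alcohol within the 2 hours prior to breath and serum collection". It applies to both phases: "The following inclusion and exclusion criteria will apply to both Specific Aim 1 and 2 of this study".

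The list of potential test confounders asks when the subject last smoked, drank and ate, and records "Time since brushing teeth, or rinsing with anything other than distilled water". Its only entry on inhaled medicine is "Nebulized inhaled medication less than 2 hours prior to breath collection".

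The demographic and clinical features, collected in both phases, include co-morbidities, "Current list of medications, including OTC and" natural remedies, and a social history of smoking, drinking and recreational drug use. None of these asks for the time of last use. Controls are matched on age, gender, ethnicity, co-morbidities, benign asbestos response and smoking status; medication use is not on that list.

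Sections G and H(3) say which laboratory's statisticians analyse which test. They describe no adjustment or sensitivity analysis using the recorded confounders.

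**The concern.** The plan accepts that a recently inhaled drug can disturb a breath measurement, but acts on one delivery device only. Pressurised and dry-powder inhalers also put drug, and in some cases propellant or excipient, into the airway that is about to be sampled. As the text would be applied at a site, use of such an inhaler minutes before collection breaks no criterion and prompts no timing entry.

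The one item that does address inhaled medicine adds little for analysis. It records an event that the exclusion criterion already rules out, so among correctly enrolled subjects it should always read 'no'. The smoking, drinking, eating and brushing items ask for time since the last event, and so still vary beyond two hours.

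At stake is the Phase 1 candidate list. If cases and controls differ in recent inhaler use, a compound from the inhaled product is associated with case status without being a product of the disease. Time of last use cannot be reliably recovered after sampling, so the sponsor would be unable to check this properly later.

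**Working it through.** **Wording, side by side**

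| Exposure | Excluded within 2 hours | Time since last use recorded |
|---|---|---|
| Smoking | yes | yes |
| Eating | yes | yes |
| Alcohol | yes | yes (last drink) |
| Brushing or rinsing | no | yes |
| Nebulized medication | yes | no, only whether under 2 hours |
| Other inhalers | no | no |

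Other inhalers are the only row with neither a restriction nor a time. The medication list should still identify current users.

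**Illustration of size.** The plan states no figure to reproduce. The group sizes come from section F: Phase 1 has 100 cases and 100 controls ("A total of 200 volunteers - 100 with objective evidence of exposure to asbestos and no evidence of mesothelioma"), and Phase 2 has 35 cases and 65 controls. Everything else is assumed: the share with recent inhaler use (p1 in cases, p0 in controls), and the rise d, in SD units, that recent use causes in a compound otherwise unrelated to disease.

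- Expected difference: D = (p1 − p0) × d
- Variance in each group: V = 1 + d² × p(1 − p)
- Standard error: SE = √(V1/n1 + V0/n0), and z = D/SE
- Chance of two-sided p<0.05: Φ(z − 1.96), plus a negligible opposite tail

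For 30% v 10% and d = 2, D = 0.20 × 2 = 0.40, V1 = 1 + 4 × 0.21 = 1.84 and V0 = 1 + 4 × 0.09 = 1.36.
- Phase 1: SE = √(3.20/100) = 0.179, z = 2.24, chance 61% (15% for p<0.001).
- Phase 2: SE = √(1.84/35 + 1.36/65) = 0.271, z = 1.48, chance 31%.

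| Assumed use, cases v controls | Rise | D | Phase 1 z | Phase 1 p<0.05 | Phase 2 z | Phase 2 p<0.05 | Both phases |
|---|---|---|---|---|---|---|---|
| 30% v 10% | 2 SD | 0.40 | 2.24 | 61% | 1.48 | 31% | 19% |
| 20% v 5% | 2 SD | 0.30 | 1.78 | 43% | 1.18 | 22% | 9% |
| 30% v 10% | 1 SD | 0.20 | 1.32 | 26% | 0.88 | 14% | 4% |
| equal use | any | 0 | 0 | 5% | 0 | 5% | – |

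The last column is the product of the two chances, for example 0.61 × 0.31 = 0.19.

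**A different model.** Suppose instead that the compound is simply present in recent users and absent otherwise, and the two proportions are compared at 0.05. Phase 1 then gives 27% (10% v 5%), 51% (20% v 10%), 66% (15% v 5%) and 90% (20% v 5%). Phase 2 gives 18%, 30%, 41% and 64% for the same pairs. With an assumed 100 compounds and a Bonferroni level of 0.0005, the Phase 1 chances fall to 1.6%, 6.5%, 13% and 39%.

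**Discrimination.** At 30% v 10% use and d = 2, the AUC is the chance that a random case exceeds a random control:
- same use status: 0.5 × (0.3 × 0.1 + 0.7 × 0.9) = 0.330
- case used, control did not: 0.3 × 0.9 × Φ(2/√2) = 0.27 × 0.921 = 0.249
- control used, case did not: 0.7 × 0.1 × Φ(−2/√2) = 0.07 × 0.079 = 0.006

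The sum is about 0.58. However large the rise, it cannot exceed 0.33 + 0.27 = 0.60.

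**The case against.** The best case for the plan has five parts.

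1. **Inhaler users are identifiable.** The current medication list should reveal them in both phases, so a sensitivity analysis leaving out all listed users needs no new field. This stands, and a reader who infers that such subjects go entirely unflagged goes too far. What the list lacks is time of last use, which the plan's own two-hour rule treats as what matters.

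2. **Unequal use is not documented.** The documents give no inhaler rates, no data on breathlessness and no effect on any compound. Matching on co-morbidities and smoking status may narrow any gap. This stands, and the probabilities are illustrative. Matching does not cover medication or recent use, however, so it cannot be relied on to close the gap.

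3. **Validation offers some protection.** A reader might infer that Phase 2, sharing the same criteria, would confirm a spurious marker. The arithmetic does not support that. In the three graded-rise scenarios the compound misses p<0.05 in Phase 2 more often than it reaches it. Performance is judged by sensitivity, specificity and predictive values, and the study stops if predictive capability is too low. A compound with an AUC near 0.58 would look weak on those measures, although section F sets no numeric threshold. The fair statement is that Phase 2 would not reliably remove the artefact.

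4. **The nebulizer item has a use.** It documents compliance with the exclusion, and some overlap between the two lists is ordinary. This stands, but a compliance check cannot support an adjustment.

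5. **Instructions may sit elsewhere.** Section D refers to a separate application document and section H to an attached description of the sampling system. Neither is available here, so the point is limited to what this document says.

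**Conclusion.** The point holds in a limited form. Among inhaled medicines only nebulized ones are restricted before sampling. Recent use of another inhaler is permitted, its timing is not captured, and no analysis of recorded confounders is described.

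The consequence is possible rather than shown. It needs recent use to differ between cases and controls, and it needs a compound that responds to that use. Under the assumed scenarios, a single such compound has about a 26% to 61% chance of p<0.05 in Phase 1 and 14% to 31% in Phase 2; at equal use both are 5%. A stricter Phase 1 threshold lowers the risk, but the plan states none. The likely harm is a weak, misleading candidate on the Phase 1 list, not a convincing false diagnostic test.

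The change is still worth making: the plan already recognises this kind of contamination, the missing timing cannot be reliably recovered later, and the remedy is cheap.

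**What to change.** - In the list of potential test confounders, replace the nebulizer item with time since last inhaled medication of any kind, with device and product.
- In section G, pre-specify a Phase 1 sensitivity analysis that rechecks each candidate compound leaving out subjects with recent inhaled-product use. Define 'recent' before the data are examined, and state what a candidate must retain, such as direction and rank. State also that compounds attributable to inhaled products are removed from the candidate list.
- Reconcile the exclusion criterion with the confounder list, since nebulized use within two hours appears in both and other inhalers in neither. Whether the exclusion itself should change is a decision for the sponsor. The data item and the analysis do not depend on that decision and do not require any medication to be withheld.

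The cost is one reworded case-report item, one extra analysis, and slightly fewer subjects in that analysis.

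### The two-hour pre-sampling rule leaves out tooth brushing and mouth rinsing, which the plan lists as potential test confounders, and no analysis use is stated for the answers collected.

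*Combined protocol and SAP*

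**What the plan says.** The relevant text is in section F and in the lists that follow it.

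- **Exclusion Criteria.** The last item rules out "Eating, smoking, inhalation of nebulized medication or consuming alcohol within the 2 hours prior to breath and serum collection". The sentence introducing the criteria says that the "inclusion and exclusion criteria will apply to both Specific Aim 1 and 2 of this study", so the rule governs both discovery and validation.
- **Potential Test confounders.** Five items are recorded: last smoke, "When did you last drink and what was it", last food, "Time since brushing teeth, or rinsing with anything other than distilled water", and "Nebulized inhaled medication less than 2 hours prior to breath collection".
- **Case-Matched Controls.** Matching is on age, gender, ethnicity, co-morbidities, benign responses to asbestos and smoking status. Brushing, rinsing and drinks are not matching factors.
- **G. Data Analysis and H. Materials and Methods, item (3).** These assign the analyses to the two laboratories. On the step from discovery to validation they say only that "Selected biomarkers will then be used in Phase 2". Neither section says what will be done with the confounder answers.

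**The concern.** The index test is a volatile organic compound profile measured in breath, so anything recently in the mouth bears on the measurement itself. The plan recognises this by listing brushing and rinsing as potential confounders and by exempting only distilled water. Yet the rule that controls behaviour before sampling does not mention them. As written, someone who used mouthwash minutes before sampling is eligible in either phase.

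Two consequences are possible. If recent use is equally common in cases and controls, it adds variance to the affected compounds, which makes true markers harder to find in Phase 1 and can lower measured sensitivity and specificity in Phase 2. If use differs between the groups, a compound with no relation to disease can be selected in Phase 1. Blinding in Phase 2 does not address either problem, because it hides disease status and does not change what was in the mouth. The concern is limited to the breath results and to the combined breath and serum test. The documents give no reason to expect an effect on the serum assay alone.

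**Working it through.** **Step 1: set the two lists side by side.**

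| Listed potential confounder | Barred within 2 hours? |
|---|---|
| Smoking | Yes |
| Food | Yes |
| Nebulized medication | Yes |
| Drink | Alcohol only |
| Brushing or rinsing | No |

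Brushing or rinsing is the only listed item with no control at sampling. Drink is partly controlled, and how far depends on what the word means.

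**Step 2: look for another safeguard.** The matching list, section G and section H contain none.

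**Step 3: illustrate the size.** The plan gives no alpha, power, effect size or usage rate, so there is no figure of its own to reproduce. Only the group sizes come from section F: 100 and 100 in Phase 1, 35 cases and 65 controls in Phase 2. Everything else below is assumed.

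Let recent use raise an affected compound by d standard deviations, with d = 1 or 2, and let a proportion p of a group be recent users. The group variance is 1 + d²p(1 − p), and the spurious case-control shift is d(p₁ − p₀).

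*Equal use, p = 0.30 in both groups.* There is no shift.
- d = 1: variance 1 + 0.21 = 1.21; effective sample loss 1 − 1/1.21 = 17%.
- d = 2: variance 1 + 4 × 0.21 = 1.84; loss 1 − 1/1.84 = 46%.

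These losses apply to each affected compound, not to the whole study.

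*Unequal use, 40% of cases and 20% of controls, 100 per group, two-sided 5% per compound.*
- d = 1: shift 0.20; SE = √((1.24 + 1.16)/100) = 0.155; ratio 1.29; selection probability 25%.
- d = 2: shift 0.40; SE = √((1.96 + 1.64)/100) = 0.190; ratio 2.11; selection probability 56%.

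With an assumed Bonferroni correction for 100 compounds (0.05/100 = 0.0005), the same probabilities fall to about 1.4% and 8.5%.

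*Would such a false marker look good in Phase 2?* Its AUC is 0.32·Φ(d/√2) + 0.12·Φ(−d/√2) + 0.28. The weights are 0.4 × 0.8, 0.6 × 0.2 and half of (0.4 × 0.2 + 0.6 × 0.8). This gives about 0.55 for d = 1 and 0.58 for d = 2, which is poor discrimination even if the same imbalance recurs.

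*Dilution of a true marker in Phase 2.* Assume 80% sensitivity and specificity, falling to 50% in affected samples. With a fraction q affected, each becomes 0.8(1 − q) + 0.5q.

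| q | Affected cases of 35 | Affected controls of 65 | Sensitivity and specificity |
|---|---|---|---|
| 10% | 3.5 | 6.5 | 77% |
| 20% | 7 | 13 | 74% |
| 30% | 10.5 | 19.5 | 71% |
| 50% | 17.5 | 32.5 | 65% |

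Exact 95% intervals around an observed 80% are 63% to 92% for 28 of 35 cases and 68% to 89% for 52 of 65 controls. A fall to 71% would therefore be hard to recognise from the Phase 2 results alone.

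**The case against.** The strongest reply is that recording a confounder is a legitimate alternative to banning it. Timing is collected for every participant, so affected samples can be identified and then set aside, resampled, modelled, or reported with and without, all without unblinding. That is correct, and a reader who infers that Phase 2 cannot be protected goes too far. What remains is that the plan commits to none of these uses.

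Other stronger readings also fail:

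- **That contaminated samples do enter the study.** The documents show only that they are permitted. They call these confounders potential, and give no rate of recent use.
- **That a mouth-product compound would be selected and then validated.** This needs a case-control imbalance in Phase 1 that recurs in Phase 2. Nothing in the plan suggests different instructions by group. Even then, the AUC of 0.55 to 0.58 would look nearly useless, and section F stops the study if predictive capability is too low.
- **That non-alcoholic drinks are certainly a gap.** The drink question may mean alcohol, since drinking appears beside smoking and drug use in the social history. The matching form of the question on food favours any beverage. The point is open, but brushing and rinsing do not depend on it.

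Preparation instructions might also exist in the IRB application or the breath-sampling guide that the plan refers to. That cannot be checked here. If they do exist, the eligibility rule should still agree with them.

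**Conclusion.** The mismatch is real and small. Brushing and rinsing are named as potential confounders, are left uncontrolled up to breath sampling in both phases, and have no stated analysis use. The same holds for non-alcoholic drinks if the drink question covers any beverage.

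The likely harm is avoidable noise in the affected compounds; bias in marker selection is possible only if recent use differs between cases and controls. No size can be established from the documents. The illustrative figures rest entirely on assumed usage rates and effects, and the 25% to 56% false-selection range also rests on an uncorrected 5% test per compound. This is a worthwhile improvement to sample collection, not a threat to the design.

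**What to change.** 1. Extend the last item of the Exclusion Criteria, for breath collection in both phases, to cover tooth brushing and mouth rinsing (distilled water excepted) within the plan's existing two-hour window. The documents do not show that two hours is the right interval for these items; it is used because it is the plan's own.
2. State whether drink in the confounder list means any beverage. If it does, add drinks other than water to the same item.
3. Use the confounder questions at the visit to check compliance.
4. Before Phase 1 marker selection, write down how non-compliant samples are handled: delay or repeat sampling, or a sensitivity analysis without them. Apply the same rule unchanged in Phase 2.

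The cost is one line in the criteria, a line in the appointment instructions and a short handling rule. Participants face a minor inconvenience and an occasional wait. The questions are already asked. The change is best made before Phase 1 sampling starts, because a sample cannot be cleaned afterwards and setting samples aside is costly with only 35 cases in Phase 2.
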